- Did you find the instructions in the games easy to understand?
- Was it easy to navigate the menu?
- How do you think we can improve the menu?

- Any comments?
 - Is there anything else you want to share with us?

- List of potential questions for the caregiver.

- How often did you have to remind the participant? Was this a burden for you?
- How much assistance did you have to provide help to participants?
- Did the participant avoid, complain, or otherwise protest when it was time to play Neuro-World?
- What advice do you have for us as we move forward with this research on Neuro-World training for persons diagnosed with MCI?

12. Assessment after 24 weeks (Only Rutgers RA can perform assessment; UMass RAs will organize the overall meeting)

- After 24 weeks, all participants will be assessed with the following tests **online (via zoom)**.

Detailed steps will be the same as the baseline assessment.

RAs will generate a new form for recording 24 weeks follow-up assessment from the corresponding **Assessment Form instrument**.

[figure not shown]
Towards the Development of a Mobile-Health Technology Based on Serious Game-based Interventions in Adults with MCI outside the clinic

Purpose

The purpose of this study is to learn: 1) if Neuro-World (mobile cognitive training games) can improve the cognitive function of adults with mild cognitive impairment (MCI), 2) if we can understand the cognitive function of adults with MCI based on their performance in Neuro-World, and 3) if we can learn practical challenges that adults with MCI face while playing Neuro-World.

Neuro-World

A tablet computer with pre-installed Neuro-world cognitive training games will be provided during the study.

Eligibility

Adults with MCI are eligible for the study if you 1) have mild cognitive impairment (we will assess your impairment level for you), 2) are 55 years old or older, 3) can use a tablet independently, and 4) have access to a computer for online video communication (e.g., Zoom).

Adults with MCI CANNOT participate in this study if you have 1) another neurologic or psychiatric disorder, 2) history of traumatic brain injury, 3) uncorrected hearing or vision

impairment, 4) any significant impairment in your arms that could affect tablet use, 5) diagnosis of dementia with Lewy bodies, progressive supranuclear palsy, multiple system atrophy, or vascular parkinsonism, 6) diagnosis of dementia, and 7) participation of any other therapist-supervised cognitive training.

If you need help navigating technology (such as using Zoom or mobile apps), you can choose to have a friend or family member help you throughout this study. If you choose this option, they will be enrolled in the study with you. In that case, helpers need to 1) be 18 years or older, 2) understand your condition, and 3) can be contacted by the study team regularly. The person is not eligible if he/she 1) has been specifically hired to provide care for you and 2) has any impairments that prevent them from helping you.

Task

1. We will ask adults with MCI to do one of the following for the study (not both).

Group A: 1) We will ask you to play Neuro-World cognitive training games 30 minutes per day, twice a week for 12 weeks in your home setting. During this period, we will give you phone calls and ask if you adhere to the cognitive training and ask you to report the time of any additional cognitive and physical activities three times a week. 2) Upon completing 24 sessions, we will ask you to join online sessions (e.g., Zoom) to share your experience of using Neuro-World 3) Then, we will give you phone calls and ask if you have any significant changes in the level of daily activities for another 12 weeks and ask you to report the time of any additional cognitive and physical activities three times a week. This study lasts about six months, and you will spend about 27.2 hours in total.

Group B: 1) We will give you phone calls and ask if you have any significant changes in the level of daily activities for 12 weeks and ask you to report the time of any additional cognitive and physical activities three times a week. 2) After the 12 weeks, we will ask you to play Neuro-World cognitive training games 30 minutes per day, twice a week for 12 weeks in your home setting. During this period, they will give you phone calls and ask if you adhere to the cognitive training and ask you to report the time of any additional cognitive and physical activities three times a week. 3) Upon completing 24 sessions, we will ask you to join online sessions (e.g., Zoom) to share your experience of using Neuro-World. This study lasts about six months, and you will spend about 27.2 hours in total.

2. If helpers participate in the study, we will ask helpers to do the following for the study.

1) We will ask you to check on adults with MCI you are helping if they do not adhere to cognitive training. **2)** We will ask you to assist adults with MCI in using a tablet computer and online communication technology as necessary. **3)** During the entire study, we will ask you to report the time of any cognitive and physical activities adults with MCI engage in once per week. **4)** During the 12-week period that adults with MCI use Neuro-World, we will contact you and ask for your perspective on their adherence to Neuro-World cognitive training. **5)** During the 12-week control period, we will contact you and ask if there are any significant changes in the activities of adults with MCI. **6)** Upon the completion of 12-week Neuro-World play, we will ask you to participate in a 1:1 interview to hear your experience and opinions as a helper. This study lasts about six months, and you will spend 4.4 hours in total for an interview and follow-up calls. You may need to spend an additional 27.2 hours in total. However, you will be asked for help only when it is necessary.

Compensation:

Adults with MCI will receive \$2 after each Neuro-World play and \$34 for each suite of cognitive assessments, which amount to a total of \$150. If helpers participate in the study, helpers will receive \$1 for each week of support and \$13 for each 1:1 interview, which amounts to a total of \$50.

If you are interested in participating or want to know more, please contact the AHHA Lab [contact], [contact]).

For Adults with MCI

Thank you for speaking with us today. Before you officially enroll in this research study, I will be asking you to complete a screening questionnaire. It should take you no more than 30 minutes to complete. If you are determined ineligible to participate, your completed questionnaire will be destroyed. If you are determined eligible to participate, the completed questionnaire will become part of the study materials, and we will protect your information as confidential and safeguard it from unauthorized disclosure. Only research personnel will have access to the information contained in your screening questionnaire. If the screening questionnaire indicates that you are eligible to participate, we will proceed to obtaining your written informed consent for participation in the study. Do you have any questions?

The contacted researcher will ask the following questions regarding the inclusion criteria (2 minutes).

1. Are you 55 years old or older?
2. Can you turn on/off a smartphone or a tablet computer? Can you start an application and use it on your smartphone or a tablet computer? It is ok to receive help from your caregiver on operating your smartphone or tablet computer.
3. Do you have access to a computer for online video communication (e.g., Zoom, Microsoft Team, Google Hangouts)?

The contacted researcher will ask the following questions regarding the exclusion criteria (5 minutes).

1. Do you have diagnosed neurologic or psychiatric disorders other than mild cognitive impairment?
2. Do you have a history of diagnosed traumatic brain injury?
3. Do you have hearing or vision impairment that can hinder you from playing games?
4. Do you have any significant impairment in your arm that could affect the use of a tablet computer?
5. Do you have diagnosed dementia with Lewy bodies, progressive supranuclear palsy, multiple system atrophy, or vascular parkinsonism?
6. Do you have diagnosed dementia?
7. Are you receiving any therapist-supervised cognitive training?

For Caregivers (optional)

The contacted researcher will ask the following questions regarding the inclusion/exclusion criteria (2 minutes).

Inclusion criteria

1. Are you 18 years old or older?
2. Do you know about your care receiver's health conditions?
3. Will you be willing to be contacted by the researchers on a regular basis in case your care receiver needs external help?

Exclusion criteria

4. Are you hired to provide care for your care receiver?
5. Do you have any cognitive, behavioral, or motor impairments that can affect assisting your care receiver in the study?

ATTENTION

When you open the box, CHECK if the following items are in the box.

1. One air-filled container
2. One tablet (in the air-filled container)
3. One tablet cover (a tablet is in the cover)
4. One charger (in the air-filled container)
5. One UPS return label

Please KEEP EVERYTHING you received that includes the following.

1. One outer box
2. One air-filled container
3. One tablet
4. One tablet cover
5. One charger
6. One UPS return label

Please DO NOT START cognitive training games until the researchers contact you.

When the study is complete, the researchers will contact and ask you to return all the items. At the time, you will need to do the following.

1. Place the tablet (with its cover) in the air-filled container.
2. Place the charger in the air-filled container.

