Official Study Title:

Towards the development of a mobile-health technology designed to encourage the use of serious game-based interventions in patients with mild cognitive impairment outside the clinic

NCT Number:

NCT04920123

Document Type:

Study Protocol

Document Date:

February 05, 2025

STUDY PROTOCOL

Study Procedures:

1. [Recruitment](#)
2. [Screening](#)
3. [Informed consent obtainment](#)
4. [Random assignment into two groups](#)
5. [Assessment at baseline](#)
6. [Shipping tablet PC5. Assessment at baseline \(Only Rutgers RA can perform assessment; UMass RAs will organize the overall meeting\)](#)
7. [Tutorial for the intervention group](#)
8. [Checking compliance every week \(twice per week\)](#)
9. [Assessment after 12 weeks](#)
10. Returning tablet PC
11. Focus group (Online workshop)
12. Assessment after 24 weeks

Role Assignment

	UMass RA	Rutgers RA
Recruitment	O	O
Screening	O	O
Informed consent obtainment	O	O
Random assignment into two groups	O	X
Assessment at baseline	O (general instructions before assessment)	O (actual assessment)
Shipping tablet PC	O	X
Tutorial for the intervention group	O	X
Checking compliance every week	O	X
Assessment after 12 weeks	O (general instructions before assessment)	O (actual assessment)
Returning table PC	O	X
Focus group (Online workshop)	O	X
Assessment after 24 weeks	O (general instructions before assessment)	O (actual assessment)

1. Recruitment:

- **50** participants with Mild Cognitive Impairment (MCI) will be recruited as follows.

[figure not shown]
- Currently planned means:
 - Emailing recruitment flyers to residents in local senior centers in Amherst, MA and Union, NJ
 - Emailing recruitment flyers to support groups and conferences
 - Posting recruitment flyers on the Internet (e.g., ClinicalTrials.gov, National Alliance on Mental Illness; nami.org, Alzheimer's Association; alz.org, UMass newsletter)
 - Posting an abbreviated recruiting message + screen shots of flyers on the social media (e.g., Facebook, Twitter)
 - Recruiting message: *"If you believe you have mild cognitive impairment, and are interested in cognitive training using mobile games, please contact AHHA Lab [contact], [contact].)"*
 - Visit senior villages
- Optional means:
 - Using paid third-party services that perform the recruiting process
 - Advertising on local newspapers

- The flyer can be found in [**Appendix 1**](#). (unified phone number / email address)

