- Available recruitment methods (website, social media group) are listed in the spreadsheet **(Patient Recruitment/Contact Information.xlsx)**

2. Screening (Both UMass & Rutgers RA can perform)

- When a volunteer contacts us through AHHA lab's email or phone number, their **name**, **phone number**, and **email** will be collected using email reply (email) or pre-recorded voicemail instruction (phone).
 - UMass and Rutgers RAs will check the email and the voicemail box regularly (1 time a week by each RA). The following is an example.
 - Rutgers RA: Mon
 - UMass RA1: Wed
 - UMass RA2: Fri
 - RAs will **add a new record** in the RedCap and enter the volunteer's **name** in the **Name Data instrument**, and **phone number** and **email** in the **MCI Participant Demographics instrument** of the RedCap and remove processed voicemail messages.
 - The convention for naming the study ID for a person with MCI will be, for example, **MCI21 (password for Neuro-World administration is woorisoft!@)**
 - The prefix **MCI** followed by an incrementing **number** with 0 padding for a single-digit number (e.g., **MCI02** will be assigned after **MCI01**; **MCI22** will be assigned after **MCI21**).
 - The study ID will be used for a MCI participant. In other words, an active caregiver will not be given a separate study ID.
 - If a caregiver participates in the study, RAs will enter the caregiver's **name** in the **Name Data instrument**, and **phone number** and **email** in the **Caregiver Demographics instrument** of the RedCap and remove processed voicemail messages.
 - The caregiver for the person with MCI will be given a separate study ID, for example **CARE21**.
 - The prefix CARE followed by an incrementing number that matches that of the person with MCI. (record in the **Caregiver Demographics instrument**)

Logged in as [name] | Log out

My Projects

REDCap Messenger

Project Home and Design

- Project Home
- Project Setup
- Designer
- Dictionary
- Codebook

Project status: **Production**

Data Collection

- Record Status Dashboard
- Add / Edit Records**
- Study ID **MCI1**
- Select other record

Applications

- Project Dashboards
- Alerts & Notifications
- Calendar
- Data Exports, Reports, and Stats

Record Home Page

The grid below displays the form-by-form progress of data entered for the currently selected record. You may click on the colored status icons to access that form/event.

Choose action for record

Study ID MCI1

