- If both the volunteer and the active caregiver have time,
 - The RA will give the volunteer and the active caregiver to read the informed consent form.
 - The RA will answer questions should the volunteer and the active caregiver have any.
 - When the volunteer and the active caregiver sign (using **DocuSign**) and return the signed informed consent form,
 - The RA will enter the date the forms are received.
 - The RA will change **the Form Status field of the Informed Consent instrument** to Complete.
 - The signed informed consent will be stored in the UMass-supported cloud (i.e., OneDrive).
 - The RA will schedule an assessment with the volunteer and the active caregiver for the baseline assessment when one UMass RA, the Rutgers RA, the volunteer, and the active caregiver are available for 2 hours in a row (AHHA lab account, [contact]).
 - The RA will mark the scheduled assessment on the Google calendar.

- If the volunteer or the active caregiver do not have time,
 - The RA will schedule an appointment when any of the RAs are available based on the Google calendar (AHHA lab account, [contact]).
 - The RA will inform other RAs of the scheduled appointment in the Slack channel.

- (When an RA is making a separate call) An RA, who is available at the scheduled appointment time, will call the volunteer, assuming that the active caregiver accompanies the volunteer.

- The RA will give the volunteer and the active caregiver time to read the informed consent form.

- The RA will answer questions should the volunteer or the active caregiver have any.
- When the volunteer and the active caregiver sign and return the signed informed consent form,
 - The RA will enter the date the forms are received.
 - The RA will change **the Form Status field of the Informed Consent instrument** to Complete.
 - The signed informed consent will be stored in the UMass-supported cloud (i.e., OneDrive).
 - The RA will schedule an assessment with the volunteer (optionally, and the active caregiver) for the baseline assessment when one UMass RA, the Rutgers RA, the volunteer, and the active caregiver are available for 2 hours in a row (AHHA lab account, [contact]).
 - The RA will mark the scheduled assessment on the Google calendar.

4. Random assignment into two groups (Only UMass RA can perform)

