 - The volunteer will join the meeting at the scheduled time.
 - The UMass RA will explain about the assessment.
 - Message:
 - Group A: "*OK. I will give the overall process of our study first. Our study participants are divided randomly into Group A/B. You are selected as Group A. It means that for the first 12 weeks, you play a cognitive game with the provided tablet PC. We will also follow up on your game playing experience and your cognitive and physical activity by call and email survey. They will be very brief and take about 1 min. After 12 weeks, you need to return a table PC, and do the second assessment, and don't need to do anything particular for the next 12 weeks. We will just check your cognitive and physical activity. For this assessment, an important note is that [Rutgers RA] should not know about which group you are in. Please know that [Rutgers RA] is only here for the assessment purpose. To assess your cognitive function without any bias, [Rutgers RA] should not know which group you are in, you already received a table PC, and start to play a game soon. So, if you have any concerns or questions related to our overall study procedure, game play or tablet PC, please feel free to talk to me or ask me. {optional} For today's assessment, [Helper Name] will be asked survey questions related to [participant name]'s daily activity first before starting cognitive assessment. I will break a zoom room for [participant name] during the survey, and let [participant name] join again after completing the survey. [participant name], do you feel comfortable with using zoom? After completing the survey, [helper name] please stay in the house but not in the room during the assessments.} The entire assessment will be video-recorded for future reference. Now the [Rutgers RA] will join and start the assessment. I will stay muted until the assessment is over, but if you have a question, please feel free to ask me.*

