- A UMass RA will ship a tablet computer, a return label, and a hardcopy instruction for returning the tablet computer to the participant's address.

- The UMass RA will generate the shipping label using the UMass paying account (**F2E075**) and the participant's address stored in **the Address to ship the tablet computer field of the MCI Participant Demographics instrument**.
 - <https://www.easyship.com/blog/prepaid-return-labels>
 - <https://www.ups.com/us/en/campusship-support/return-services.page>
- The UMass RA will generate the returning label.
- The UMass RA will perform a factory reset on a tablet computer to be shipped.
- The UMass RA will perform all the updates.
- The UMass RA will install Neuro-World.
- The UMass RA will enter the study ID in Neuro-World.
- The UMass RA will double-check to make sure Neuro-World works as expected.
- The UMass RA will print out the instructions.
- The UMass RA will wrap the tablet + plastic case in a bubble wrap, put it in the air-inflated laptop package, and put it in the box.
- The UMass RA will put the printed instructions and the returning label in the box.
- The UMass RA will seal the box using scotch tape.
- The UMass RA will put a shipping label on the box and place it in the on-campus UPS pick-up location.
- The UMass RA will text and email both the participant and the caregiver about the estimated delivery date.
- The UMass RA will enter the shipped date, and the tracking number in **the Shipped Date field** (both **Shipping to the subject from the UMass**, **Returning to the UMass from the subject**) of **the Tablet Ship & Return instrument**.

- A UMass RA will track the delivery of the tablet computer.

- The UMass RA, on his/her assigned date, will check if any of the tablet computers are estimated to have arrived.
- The UMass RA tracks the delivery using the tracking number.
- If the package is reported to be delivered,
 - The UMass RA will call the participant (the caregiver if the participant cannot be reached) and confirm the delivery.
 - If the participant (or the caregiver) confirms the receipt of the tablet computer,
 - The UMass RA will schedule a tutorial session when the participant, the caregiver, and one UMass RA are available based on the Google calendar.
(AHHA lab account, [contact])
 - The UMass RA will notify the responsible UMass RA for the tutorial (the UMass RA, who schedules the tutorial session, may not be the one who is available for the tutorial session).

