- The researcher (i.e., a UMass RA) will contact the participant or the caregiver separately to ask about any potential issues.
- Should they have any questions, the participant or the caregiver can contact the UMass RA anytime through a phone call or an email to schedule a meeting. → Zoom link will be sent at a scheduled time. Video-record interactions.

- The UMass RA will store the video-recording in the MS OneDrive

- The UMass RA will initially store the Zoom video-recording in the encrypted & password-protected local computer.
- The UMass RA will upload the file to the HIPAA-compliant cloud storage supported by UMass Amherst (MS OneDrive)
- The UMass RA will remove the file from the local computer.

8. Checking compliance every week (UMass RA will perform)

- UMass RAs will follow up with the participant twice a week for 24 weeks by phone call.
- If the caregiver participates in the study, UMass RAs will follow up with the caregiver once a week for 24 weeks by phone call.

- The phone follow-up will be audio-recorded.
- For the participant,
 - During the experiment period
 - When the participant successfully adheres to Neuro-World training, a casual follow-up.
 - Message: "*How is Neuro-World training going?* Are there any significant changes in your daily activities? Could you explain in more detail? Thank you."
 - When the participant missed Neuro-World training this week, try to understand what hinders the participant's low adherence.
 - Message: "I noticed that you have not played Neuro-World this week. Is everything ok? Do you need any help?"
 - At the last follow-up call, ask the participant to return the tablet computer & arrange the 1:1 interview.
 - Message: "So, this week is your last Neuro-World training. Would you be able to return the tablet computer? Please wrap the tablet computer using bubble wrap. Put the wrapped tablet computer and the charger in the air-inflated package. Put the package in the paper box. Put the returning label on the box."
 - The RA will schedule the earliest available time for the participant and both UMass RAs.
(AHHA lab account, [contact])
 - For more details about the interview, refer to **11. Interview**.
 - During the control period
 - Message: (for MCI participant) "Are there any significant changes in your daily activities? Could you explain in more detail? Thank you."

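### Assessor masking protects the allocation record but leaves three communication routes (in-session questions, lab calendar, lab mailbox) by which a participant's group could reach the only outcome rater

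*Protocol*

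**What the plan says.** **The requirement.** Protocol section 5 (Assessment at baseline) has the UMass RA tell each participant: "To assess your cognitive function without any bias, [Rutgers RA] should not know which group you are in". The Group B script carries the same message. Under sections 5, 9 and 12 only the Rutgers RA may assess, at baseline, week 12 and week 24, and section 5 has that RA score during administration.

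**The safeguards.** The Role Assignment table keeps the Rutgers RA out of randomisation, tablet shipping, tutorials, compliance checks, tablet return and the focus group. Section 4 hides the Randomization instrument from Rutgers and restricts the allocation folder to UMass RAs. Section 5 keeps the assessor in a breakout room while the group is discussed.

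**The three places at issue.**
- *Script, section 5.* Just before the assessor is brought in, the UMass RA says: "I will stay muted until the assessment is over, but if you have a question, please feel free to ask me". The Group B wording is nearly identical. Sections 9 and 12 repeat the baseline steps.
- *Calendar, sections 3 and 6.* For the baseline assessment, "The RA will mark the scheduled assessment on the Google calendar". For the tablet tutorial, "The UMass RA will schedule a tutorial session when the participant, the caregiver, and one UMass RA are available based on the Google calendar". Both passages name the AHHA lab account. Section 8 names it again for scheduling the end-of-training interview.
- *Mailbox and voicemail, sections 1, 2 and 7.* Section 2 states: "UMass and Rutgers RAs will check the email and the voicemail box regularly (1 time a week by each RA"), with Monday as the example for Rutgers. The item opens "When a volunteer contacts us through AHHA lab's email or phone number". Section 1 describes the flyer as carrying a "unified phone number / email address". Section 7 tells people about to start training that "the participant or the caregiver can contact the UMass RA anytime through a phone call or an email", in order to arrange a meeting.

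**The concern.** Participants know their own allocation and the comparator has no sham game, so a masked assessor is the main protection against expectation affecting the rater-scored tests. Four of the seven outcomes in SAP section 2 (MoCA, MMSE, DFS, DBS) are performance tests given and scored by this one person. A rater who knows who has just finished the game period could prompt or score differently without intending to.

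The SAP tests one-sidedly, at 0.05, for improvement with the intervention. A rating shift in favour of the game period would therefore count as benefit, and nothing in the analysis would separate it from a real effect. The safeguards cover the allocation record and what participants are told before the assessment. They do not cover the channels through which the trial's daily business passes.

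**Working it through.** The plan gives no figure to reproduce here. The check follows each route through the text and separates what is stated from what must be assumed.

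**1. In-session questions.** The order of events in section 5 is:
1. The assessor waits in a breakout room. The UMass RA states the group and offers to take questions about the study, the game or the tablet. This invitation is safe, because the assessor cannot hear it.
2. The UMass RA adds that, though muted, they can be asked a question. No topic is excluded.
3. The assessor is brought back, recording starts, and the assessment runs.
4. The assessor leaves. The UMass RA then asks for questions.

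The invitation in step 2 takes effect in step 3, when the assessor is present. It comes from the person just named as the contact for game and tablet questions. At baseline nobody has played. At week 12 Group A has and Group B has not, so one remark about playing is enough. By week 24 both groups have played, so a remark would have to show how recently. This route needs no assumption about access, only that a participant takes up the offer with a revealing question.

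**2. Calendar.** There are two sequences, game then control (A) and control then game (B). A tutorial precedes the game period, so its date falls near the start for A and near week 12 for B. One dated entry tied to a participant identifies the sequence, and with it both periods.
- Stated: tutorials, consent calls and assessments are scheduled through the same lab account. Consent calls may use any RA's availability, and baseline assessments need the Rutgers RA's.
- Not stated: that tutorials are entered on that calendar, how they would be labelled, or whether Rutgers can view them.

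**3. Mailbox and voicemail.**
- Stated: the Rutgers RA checks both weekly, and no end date is given. Recruitment runs to 50 people, each followed for 24 weeks, so late recruitment can overlap earlier participants' follow-up.
- Not stated: which number or address enrolled participants use to reach the UMass RA, or that it differs from the lab line.
- For disclosure, a participant must use the lab line, and the message must mention the game or tablet.

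**4. Size.** Let u be the share of end-of-game-period ratings made with knowledge of group, and b the average shift that knowledge causes. Suppose other ratings are unaffected. The SAP pairs changes between periods without giving the formula, so two readings are possible:
- *End-of-period scores, game minus control:* the bias is u × b in both groups.
- *Within-period changes, game minus control:* in Group A, (Y12 − Y0) − (Y24 − Y12) = 2·Y12 − Y0 − Y24, so the bias is 2 × u × b. In Group B, (Y24 − Y12) − (Y12 − Y0) = Y24 − 2·Y12 + Y0, so the bias is u × b.

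If b favours the game, the bias does so under both readings. The documents give neither u nor b, so no number of points follows.

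**The case against.** The case against is substantial, and several parts of it stand.

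- *The rota is recruitment intake.* It sits under Screening, concerns volunteers, and its task is to record contact details and clear voicemail. The unified contact is a feature of the flyer. This stands: the text does not say that enrolled participants' messages arrive there.
- *Section 7 points to the UMass RA.* The contact it describes is a request for a meeting, followed by a Zoom link. This stands too. The consent form is not in the text reviewed and may name a contact. What remains is that no separate contact is stated and the rota has no end.
- *Only assessments are expressly marked on the calendar.* For tutorials the text says only that the time is chosen from it. This stands, so the calendar route must be put conditionally.
- *The game and tablet invitation is given out of the assessor's hearing, with a warning about masking.* True. But the later, unrestricted invitation applies while the assessor is present. It relies on people with cognitive impairment to judge which questions are safe to ask.
- *Masking is clearly deliberate.* Agreed. The role table, the hidden instrument and the restricted folder are sound. They do not govern these three channels.

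A reader might go further and infer that the assessor reads participants' messages every week and sees their tutorials on the calendar, so that masking fails for each participant. The documents do not support that. They do not state that assessors have such access, and the mailbox route depends on who writes or calls.

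**Conclusion.** The point holds as a conditional risk. The in-session route follows directly from the script and recurs at both follow-up assessments. The calendar route holds if tutorials are entered where Rutgers can see them. The mailbox route holds if the rota continues during follow-up and enrolled participants use the lab contact.

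Nothing in the documents shows that unmasking has occurred. It is tempting to attach a bias in MoCA points, or to count weekly mailbox checks as exposures. Neither is justified: u and b have no source in the documents, and a check is not a disclosure. Only the direction can be stated, and only on the assumption that a rater who knows the group leans towards the intervention. This is a cheap improvement to make, not a defect that invalidates the design.

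**What to change.** 1. **Script.** In both group scripts, and so at all three assessments, replace the offer to take questions while muted with a request to hold any question about the study, the game or the tablet until the Rutgers RA has left. Section 5 already has a question slot at that point.
2. **Calendar.** Keep tutorials and interviews on a calendar open to UMass only, and share only assessment slots with Rutgers.
3. **Mailbox and voicemail.** Take the Rutgers RA off the rota; the example rota already has UMass RAs on Wednesday and Friday. Alternatively, give enrolled participants a UMass-only number and address.

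The cost is a few lines of protocol text, a second calendar and possibly a second contact point. If the Rutgers RA leaves the rota, the mailbox is checked twice a week instead of three times in the example schedule, so some recruitment enquiries wait a little longer. Design, sample size and analysis are unchanged.

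Two optional additions would show whether masking held. The assessor could record a guess of group after the week 12 and week 24 assessments. The session recordings, which start when the assessor rejoins, could be checked for revealing questions; this also works for sessions already held.
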